#### **Quantitative Analysis**

We will conduct descriptive analyses and multivariate modeling of patient self-report and administrative data to examine changes in outcomes over time and explore moderating variables. If any additional analyses are identified during the study, they will clearly be labeled as post-hoc comparisons and interpreted as such.

Primary outcomes will be analyzed using both self-report and claims data. As such, loss to follow-up for a participant will be calculated at the point which they no longer complete their self- report questionnaires for a given timepoint and they are no longer Medicaid/Medicare-Medicaid eligible, as determined by the proxy of 9 months of Medicaid/Medicaid-Medicare coverage in the 12-month period prior to the data collection timepoint. Whichever comes last is the point at which the participant is lost to follow-up. No surveys are collected during Timepoint 2, and as such, loss to follow-up will be calculated at the point which they are no longer Medicaid/Medicare-Medicaid eligible, as determined by our proxy described above.

All inferential modeling will be preceded by descriptive analyses of baseline and outcome measures. Summary statistics will include the mean and standard deviation, and the median and range for continuous variables, and the frequency and percentage for each categorical variable. Results will be presented for the entire sample and stratified by intervention arm. We will also statistically assess the balance of key covariates across the interventions via analysis of variance for continuous measures and chi-squared tests for categorical measures. For continuous variables which are assumed to be normal, we will visually assess the univariate distribution via a normal probability plot to determine departure from normality and the bivariate correlations between pairs of covariates to assess collinearity; appropriate diagnostics for collinearity and model fit of the regression models described below will also be checked in each analysis. Transformations will be implemented if required, although slight to moderate departures from normality will not be problematic with the large sample sizes.

Our models will be based on an intent-to-treat principle as we do not expect large drop out or non-adherence. We will employ linear regression models for continuous outcomes, logistic regression for dichotomous outcomes, and Poisson regression or negative binomial models (in the case of over-inflated variance) for count outcomes. We will fit multivariate models with the key independent variable of interest being the main effect of treatment with main effects for additional covariates included to produce an adjusted estimate of the treatment effect. These covariates will be defined a priori and will be divided into two subgroups. The first set of clinically-important covariates will be included in all models including age, race, gender, insurance type, illness complexity, and socio-economic status. The second set of covariates will be defined as engagement in interventions, social support, health literacy, and technology literacy. To address Aim 2, separate models will be fit for each a priori defined heterogeneity of treatment group (HTE) subgroup of interest. As listed below, we will test the interaction of treatment with the covariate defining the HTE subgroup.

The objective of Aim 2 is to determine whether the intervention works better for some than for others. Our pre-specified analysis plan will examine differences in main outcomes for

several subgroups. These subgroups are determined by our stakeholders to be most relevant so that end results can meaningfully inform patients about what works best for whom, and in turn, better supports individuals with MCC as they navigate the health care system and make decisions about their care. Furthermore, in examining differential impact of the interventions based on these subgroups, providers, payers, and other decision makers can target resources in a manner that best meets the needs of those in services, reduces variations in practice, and improves health outcomes.

We are only powering for the interactions with age, since we do not have any a-priori hypotheses about subgroup effects for the other variables. Those additional subgroups will clearly be labeled as exploratory and will only be examined further if the overall analysis is significant. We will conduct modeling as defined above to examine the HTE and will utilize contrasts from these regression models to make inferences about the heterogeneity. We will present both the treatment effect estimates, in terms of estimated odds or risk ratios for dichotomous or rate outcomes or the model coefficients for the continuous outcomes and measures of their variability in the form of confidence intervals. Two-sided tests of level 0.05 of the interactions between intervention and HTE subgroup will allow us to test the Aim 2 hypotheses.

For all the described models, we will focus on the 12-month outcome. Each of the above analyses will also be repeated using all follow-up outcomes collected as a secondary analysis using a mixed model with a random intercept to account for within-subject repeated measures and associated correlation. Significance tests from all regression models will all be assessed using likelihood ratio tests for logistic, Poisson, or, if applicable, negative binomial models or partial F-tests for linear regression.

Additionally, exploratory data analyses will include comparison of the following variables in the pre- versus post-COVID-19 time periods: a) demographics and primary outcomes at baseline, b) the primary outcomes over time, and c) patterns in missing data. If significant differences result, we will repeat the primary analysis by: a) adjusting for the demographic variables that can describe pre- and post-COVID-19 participants, b) include indicator variables for post-COVID-19 enrollment with and without interactions with time variables, and c) statistically account for missing patterns.

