#### **Primary Outcome Measures**

Patient activation will be assessed using the Patient Activation Measure (PAM), a 13-item scale that gauges individual knowledge, skills, and confidence essential to managing one's own health. In consideration of "straight-lined" answers in the PAM measure, (i.e., all 13 questions answered with "strongly disagree"), we plan to include all participant responses and conduct a sensitivity analysis. This is recommended by our study investigative team, including our Patient Partner Co-investigator.

Health status will be measured using the Health Survey (SF-36), a 36-item scale measuring functional health and well-being within eight domains, including physical functioning, physical ability to complete tasks, bodily pain, general health, vitality, social functioning, emotional ability to complete tasks, and mental health.

Subsequent 90-day rehospitalization will be measured using an all-cause readmission rate existing in UPMC ISD inpatient claims for physical and behavioral health service use within 90 days of the last hospital discharge prior to study enrollment. All-cause readmission does not include observation visits.

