## **Secondary Outcome Measures**

Subsequent rehospitalization will be measured using an all-cause readmission rate existing in UPMC ISD inpatient claims for physical and behavioral health service use within 30 days and again at 12 months, following the index inpatient admission. Inpatient and ED visits that were adjudicated and reclassified as Observation visits will be separately explored at 12 months.

Functional status will be measured using the PROMIS Physical Functional Form – Short For 6b which is a brief self-report tool that assesses functional impairment in everyday tasks, household chores, and walking using a 5 point Likert scale.

Quality of life will be measured using the Quality of Life Enjoyment and Satisfaction Questionnaire (Q-LES-Q-18), which is an 18-item, self-administered questionnaire monitoring enjoyment in several domains (physical health, subjective feelings, leisure time activities, social relationships).

Care satisfaction will be measured using the Patient Assessment of Chronic Illness Care (PACIC), a 20-item survey designed to provide an assessment of important aspects of care for chronic illness patients, including specific actions or qualities of care that patients report experiencing in the service delivery system and their satisfaction level.

Emergent care use will be measured using existing behavioral and physical health claims data from the UPMC ISD data warehouse determining participant frequency of emergent service use over 12 months.

Engagement in primary, specialty, mental health care will be measured using existing behavioral and physical health claims data from the UPMC ISD data warehouse determining participant frequency of non-acute visits for participants over 12 months.

Gaps in care will be assessed using Healthcare Effectiveness Data and Information Set (HEDIS) quality metrics that will be compiled using existing behavioral and physical health claims data from the UPMC ISD data warehouse. Gaps in care will be assessed for six of the most common chronic diseases present among our target population, including: asthma, chronic obstructive pulmonary disease, congestive heart failure, coronary artery disease, diabetes, and depression.

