# Inclusion/Exclusion Criteria

## **Inclusion Criteria**

Individuals who are (1) Medicaid or dual-eligible; (2) age 21 years and older; (3) insured through physical and/or behavioral health payers within the UPMC ISD; (4) identified as members high risk for high utilization including rehospitalization and have had an inpatient hospital stay within the last 30 days; (5) who have at least one physical health condition (e.g. cardiovascular disease, hypertension, COPD, diabetes) and at least one additional physical or behavioral health condition (e.g. depression, serious mental illness, substance abuse disorder); and (6) who reside in Pennsylvania.

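### Follow-up for the claims outcomes is judged by Medicaid coverage, not by enrolment in the UPMC ISD plan whose claims supply those outcomes

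*Combined protocol and SAP*

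**What the plan says.** **Follow-up rule (Quantitative Analysis).** A participant is lost once two things have happened: self-report questionnaires have stopped and, on the coverage side, "they are no longer Medicaid/Medicare-Medicaid eligible, as determined by the proxy of 9 months of Medicaid/Medicaid-Medicare coverage", counted over the 12 months before each timepoint. On combining the two, the section says: "Whichever comes last is the point at which the participant is lost to follow-up". The proxy names no plan or payer, and the section does not say which files the coverage months are read from.

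**Outcome source.** Under Primary Outcome Measures, the readmission measure is an "all-cause readmission rate existing in UPMC ISD inpatient claims for physical and behavioral health service use within 90 days", counted from the most recent discharge before enrolment. Under Secondary Outcome Measures, readmission is taken from the same claims "within 30 days and again at 12 months, following the index inpatient admission". Emergent care and non-acute visits over 12 months, and gaps in care, come from the UPMC ISD data warehouse.

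**Entry.** The Inclusion Criteria list Medicaid or dual eligibility as item 1 and, separately as item 3, being "insured through physical and/or behavioral health payers within the UPMC ISD". Nothing requires or tracks item 3 after entry.

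**Analysis.** The plan names intention-to-treat, logistic models for dichotomous outcomes, and Poisson or negative binomial models for counts. It gives no person-time offset, no censoring rule and no coding rule for a participant without UPMC ISD coverage in the outcome window. Missing-data patterns are mentioned only in the exploratory COVID-19 work, and an adjustment for them follows only if differences are found.

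**The concern.** The Inclusion Criteria treat programme eligibility and plan membership as two different things. The follow-up rule tests the first, while the outcomes can be seen only through the second. Someone who stays on Medicaid but moves to another insurer can satisfy the rule, although admissions paid only by the new insurer cannot appear in the outcome source. An absent claim carries no missing-value flag, so unless a rule says otherwise it reads as zero.

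If leaving is equal across arms, observed rates and differences shrink. If it is unequal, the comparison is biased. The plan does not report leaving by arm, so a reader could not tell which had happened.

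**Working it through.** **1. The plan's own figure.** Inputs from Sample Size and Power Calculations: 20% v 28%, 448 per active arm, two-sample test of proportions. A two-sided 5% level is stated only for the interaction tests and is assumed here.

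- Mean rate: (0.20 + 0.28)/2 = 0.24.
- Null standard error: √(2 × 0.24 × 0.76/448) = 0.02854.
- Alternative standard error: √((0.20 × 0.80 + 0.28 × 0.72)/448) = 0.02841.
- Power: Φ((0.08 − 1.96 × 0.02854)/0.02841) = Φ(0.847) = 80.2%.

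The stated 80% is reproduced. It takes readmission as fully observed in all 448.

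**2. What the proxy can detect if coverage months do come from UPMC ISD files.** Nine of the previous 12 months are needed. Take a participant fully covered before enrolment:

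| Timepoint | Months before enrolment in look-back | Months after enrolment needed to pass |
|---|---|---|
| 3 months | 9 | 9 − 9 = 0 |
| 6 months | 6 | 9 − 6 = 3 |
| 12 months | 0 | 9, so a gap of 12 − 9 = 3 is allowed |

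A person who leaves directly after randomisation can still pass at 3 months. If the months are read from a wider Medicaid source, a plan change is not detected at all. Under either reading, a participant who keeps completing surveys is not lost, because the later of the two losses counts.

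**3. Which windows are exposed.** The primary window runs 90 days from a discharge before enrolment, and entry requires an inpatient stay within the last 30 days. About 90 − 30 = 60 to 90 days therefore remain after enrolment, and only plan changes in that time affect the measure. The 12-month readmission, emergent-care and visit outcomes are exposed for the whole year. Hypothesis 1a also refers to readmission at 12 months.

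**4. Size, with an assumed share.** Let m be the share of true readmissions absent from UPMC ISD claims and read as none, so that observed rate = true rate × (1 − m). The documents give no m. As a guide, m = 5% would arise if 10% left and half of their readmissions fell after leaving (0.10 × 0.5), and m = 10% if 20% left (0.20 × 0.5).

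| m, equal in both arms | Observed rates | Difference (points) | Power | Power if that share of participants is removed instead |
|---|---|---|---|---|
| 0% | 20.0% v 28.0% | 8.0 | 80.2% | 80.2% |
| 5% | 19.0% v 26.6% | 7.6 | 77.5% | 78.1% |
| 10% | 18.0% v 25.2% | 7.2 | 74.6% | 75.9% |

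The last column keeps the rates at 20% and 28% and counts the removal as loss beyond the planned 20% attrition.

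**5. Unequal m, also assumed.**

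- 0% unseen in High-Touch and 10% in High-Tech: 20.0% v 25.2%, a difference of 5.2 points.
- The reverse: 18.0% v 28.0%, a difference of 10.0 points.
- No true effect (24% in both arms) with 0% v 10% unseen: 24.0% v 21.6%, a false difference of 2.4 points. The chance of significance in that direction is about 13.5%, against a nominal 2.5%.

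**The case against.** The strongest defence is that UPMC ISD is the only claims or administrative source the documents name, so the coverage months may well be counted in its own files. Leaving the plan would then stop the count. This is a fair reading and it makes the problem smaller, but the look-back in step 2 shows that it does not remove it.

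Four stronger readings are tempting, and the documents do not support them:

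- **That the plan scores leavers as event-free.** No section says so. The plan has no rule for absent claims; reading them as zero is the likely default, not a stated choice. Nor does any section link the loss-to-follow-up definition to outcome coding.
- **That every later admission disappears.** Entry is allowed through physical and/or behavioral payers, so a member who leaves one UPMC ISD payer may remain visible in another.
- **That leaving differs by arm.** High-Touch uses payer-employed staff intensively, but Community Team staff also serve High-Tech and ODP. Differential leaving is conjecture, and step 5 shows only what it would do.
- **That a fifth of participants could have the whole window unseen** (16.0% v 22.4%, power 68.2%). This cannot occur for the 90-day measure, whose window opens before enrolment, when UPMC ISD insurance is an entry condition.

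It is also fair to say that translating time unseen into readmissions unseen assumes an even readmission rate over the window, which the documents do not state.

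**Conclusion.** The point holds as a gap in the follow-up definition: the stated rule does not test whether a claims outcome can be observed, and no rule covers time when it cannot. The weight falls on the 12-month claims outcomes; the 90-day primary measure is less exposed.

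With equal leaving the cost is modest, a loss of about 3 to 6 points of power over the assumed range, and most of that loss would remain if the same participants were removed. The main reason to act is bias. Unequal leaving could move the difference either way, and the plan as written would not show it. The size is unknown because the documents give no rate of leaving the plan.

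**What to change.** In Quantitative Analysis:

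1. Define follow-up for claims outcomes separately from survey follow-up, so that the later-of-the-two rule does not apply to them.
2. Base it on month-by-month enrolment in the UPMC ISD plan whose claims supply the outcome, within that outcome's window.
3. Treat unenrolled time as unobserved, not event-free: a person-time offset for count outcomes, and censoring at leaving (in a time-to-readmission analysis) or multiple imputation for readmission.
4. Report leaving by arm.
5. Add an analysis of participants continuously enrolled over the window as a sensitivity analysis only, noting that it conditions on a post-randomisation event and can itself be biased if leaving is related to arm.

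The cost is SAP wording and the use of enrolment records that the payer should already hold. Recruitment and care do not change. The downside is that somewhat fewer participants or person-months count as followed for claims outcomes.

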## Study Design/Methodology

We have chosen an individual-level randomized design along with a pragmatic, mixed-methods approach to compare three integrated care approaches, High-Touch (in-person/telephonic supported), High-Tech (technology-supported) and ODP for Medicaid or dual-eligible adult members with MCC who reside in in Western, Central, or Eastern Pennsylvania (PA) and are at high risk for high utilization, including rehospitalization.

Quantitative data will be collected from several sources. Self-report data will be gathered at baseline and three additional timepoints (3-, 6-, 12-months) using REDCap Cloud, a secure data collection platform. Claims/administrative data will be collected from UPMC Insurance Services Division (UPMC ISD) to inform several outcomes and covariates. Claims data will be extracted at six months and 12 months to characterize participant service use through each participant's enrollment period, allowing for one full year of service-use observation.

Qualitative telephonic interviews will be conducted with a sample of participants and CT staff to examine perceived barriers and facilitators to efficient and effective implementation of the High-Touch and High-Tech approaches for delivering evidence-based integrated care at three timepoints (Participants: baseline, 3-, and 12-months; CT Staff: baseline, mid- and end-implementation period).

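### One loss-to-follow-up rule serves both survey and claims outcomes, so attrition is understated for each source, and the 12-month count models state no exposure offset

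*Combined protocol and SAP*

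**What the plan says.** The Quantitative Analysis section of the Statistical Analysis Plan notes that the primary outcomes draw on self-report and claims data, and from this derives a single rule per participant. Loss requires two things together: the person has stopped completing questionnaires, and the person is no longer covered, "as determined by the proxy of 9 months of Medicaid/Medicaid-Medicare coverage in the 12-month period prior to the data collection timepoint". On timing it says: "Whichever comes last is the point at which the participant is lost to follow-up". There is one exception. It states that "No surveys are collected during Timepoint 2", so at that timepoint the coverage proxy alone decides. No separate rule is given for secondary outcomes.

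The two kinds of outcome are observed differently:

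- **Survey.** Patient activation (PAM) and health status (SF-36) are self-report measures.
- **Claims, primary.** All-cause readmission is taken from records "existing in UPMC ISD inpatient claims for physical and behavioral health service use". Its window is the 90 days after the latest discharge that precedes entry to the study.
- **Claims, secondary.** 30-day and 12-month readmission, emergent care use over 12 months and non-acute visits over 12 months also come from the payer's claims.

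Study Design/Methodology says claims are extracted at six and 12 months to describe service use through each participant's enrollment period, "allowing for one full year of service-use observation". For analysis, the SAP names logistic regression for dichotomous outcomes and Poisson or negative binomial regression for counts, on an intent-to-treat principle. It mentions no exposure offset, no censoring at loss of coverage and no coverage condition.

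**The concern.** Whether a survey was answered says nothing about whether an admission or visit would have reached the payer's claims. Being insured does not supply a missing PAM or SF-36 score. Because the rule needs both sources to fail, either one can hide the failure of the other:

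- A person who answers the 12-month survey after losing coverage counts as followed, although claims stop when coverage stops.
- A covered person who answers no surveys counts as followed, although two of the three primary outcomes are missing.

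Two things are at stake. The first is the attrition a reader will see, which cannot exceed the smaller of the two source-specific losses wherever both conditions apply. The second is the 12-month counts. If observed time varies and the model does not account for it, fewer events and less observation look the same. That matters for the comparison if observation time differs between arms.

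**Working it through.** **1. The plan's own figure.** Inputs from Sample Size and Power Calculations: 20% v 28% readmission, 448 per active arm. Two-sided 0.05 is assumed, as the SAP states it only for the interaction tests. With pooled variance, SE0 = √(2×0.24×0.76/448) = 0.0285 and SE1 = √[(0.20×0.80 + 0.28×0.72)/448] = 0.0284. Power = Φ[(0.08 − 1.96×0.0285)/0.0284] = 80.2%. The stated 80% reproduces and is not in dispute.

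**2. Reported attrition.** The documents give no loss by source. Assume 20% survey loss (the plan's attrition figure, which it does not tie to a source) and 10% proxy failure.

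- If independent, the rule reports 0.20 × 0.10 = 2% lost: 28 of 1,400, so 1,372 followed.
- Bounds without independence: max(0, 0.20 + 0.10 − 1) = 0% to min(0.20, 0.10) = 10%.
- By source, 1,120 have surveys and 1,260 pass the proxy.

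**3. What the proxy certifies.** At 12 months the look-back coincides with the time since enrollment, so passing with 9 months leaves up to 3 unobserved. Under a constant event rate that person's claims hold 9/12 = 75% of the events. At month t < 12, the look-back includes 12 − t months before enrollment, and the post-enrollment months needed to pass are max(0, 9 − (12 − t)): 3 at six months and 0 at three months.

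**4. Equal loss, 12-month readmission.** Assume a share u of each arm loses coverage at a uniform random time, unseen stays count as no event, and the hazard is constant, L = −ln(1 − p). The planned rates are borrowed for a 12-month window. The risk seen in someone who loses coverage is s = 1 − p/L: 10.37% for p = 20% and 14.77% for p = 28%. The observed rate is (1 − u)p + u·s.

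| u | High-Touch | High-Tech | Difference | Odds ratio | Power, 448 per arm |
|---|---|---|---|---|---|
| 0% | 20.0% | 28.0% | 8.0 points | 0.643 | 80.2% |
| 10% | 19.04% | 26.68% | 7.6 points | 0.646 | 77.8% |
| 20% | 18.07% | 25.35% | 7.3 points | 0.650 | 75.3% |

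**5. Equal loss, 90-day readmission.** Entry requires an inpatient stay in the last 30 days, so the window closes about W = 60 to 90 days after enrollment. Treat all events as post-enrollment, with loss uniform over 365 days. The risk seen in someone who loses coverage is (W/365)s + (1 − W/365)p. At u = 10%:

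- W = 60: 19.84% v 27.78%, 7.94 points.
- W = 90: 19.76% v 27.67%, 7.91 points.

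**6. Unequal loss, no true effect.** Assume u = 5% v 15%.

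- Counts: mean covered time is 1 − u/2, so the ratio without an offset is 0.925/0.975 = 0.949. With log(covered time) as offset, each arm's count is divided by its own covered time and the ratio returns to 1.00, if loss is unrelated to the event rate.
- 12-month readmission at 24% in both arms: s = 12.55%, giving 23.43% v 22.28%, a spurious 1.1 points. The standard error of a difference at 448 per arm is 2.9 points, so this is about 0.4 SE.

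**7. Excluding uncovered participants instead.** At u = 10%, 403 per arm remain and power is 75.9%, below the 77.8% in step 4.

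**The case against.** The strongest reply is that the rule only labels when a person is lost. It does not say who enters a model or how unobserved claims are coded, and every bias figure above needs that coding. This stands. A reader might infer that unseen admissions are scored as no readmission, or that the rule defines the analysis set; the documents say neither.

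Second, the designated primary claims outcome is barely touched: about 7.9 instead of 8.0 points. That also stands.

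Third, bias in the comparison needs coverage loss that differs by arm. A reader might suspect that one strategy helps members keep coverage better than another, but nothing in the documents shows this, and the protocol describes both active arms as addressing the full range of health determinants. The 5% v 15% case is an assumption.

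Fourth, the plan has some compatible wording. Describing use through each participant's enrollment period could mean observation is limited to enrolled time, and the SAP refers to ratios for rate outcomes. The full year in Study Design/Methodology is something the extraction allows for, not a guarantee. These phrases fit an offset but do not state one. Likewise, the secondary random-intercept model on all follow-ups uses partial survey responders, so incomplete surveys are not wholly unaddressed. It does not resolve gaps in claims.

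Fifth, dropping uncovered people would cost more power than the flaw and would select after randomization, against the intent-to-treat principle. This is right, and it shapes the fix.

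What the reply does not remove is the rule itself, which mislabels follow-up for each source, and the missing exposure term for the 12-month counts.

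**Conclusion.** The concern holds, at minor to moderate severity, for attrition reporting and the 12-month secondary claims outcomes. Where both conditions apply, the composite rule cannot report more loss than the better-retained source has, and will usually report much less (2% in the illustration, where the sources lose 20% and 10%). The emergent-care and visit counts are modelled without a stated adjustment for covered time. With equal loss of 10%, absolute counts would be 5% too low (mean covered time 1 − 0.10/2 = 0.95) and ratios unbiased. Only loss that differs by arm would distort the comparison.

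These sizes rest on assumed loss shares, uniform loss times, constant hazards, loss unrelated to risk and, for the readmission rates, unseen stays counted as no event. The documents supply none of these, so the true size is unknown. They do not support a claim that the primary readmission result is materially biased, or that the trial is underpowered for this reason. Hypothesis 1a is worded at 12 months while the primary measure is a 90-day rate; if the 12-month reading governs, the step 4 figures apply. That mismatch is a separate matter.

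**What to change.** 1. Define and report follow-up separately by data source and by arm. For survey outcomes, use a completed survey at the timepoint. For claims outcomes, use UPMC ISD coverage over the outcome window, counted from its start and not by a 12-month look-back. A survey response should not override it.
2. Use log(covered time) as an offset in the 12-month Poisson or negative binomial models.
3. Keep the intent-to-treat logistic model for readmission as the main analysis. Add a sensitivity analysis that censors at loss of coverage, by time to first readmission or by censoring weights. Do not exclude uncovered participants from the main analysis.
4. Reconcile the statement that "No surveys are collected during Timepoint 2" with Study Design/Methodology, which schedules self-report at 3, 6 and 12 months, and with Compensation for Participation, which pays for 3-month self-report measures as Timepoint 2.

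The cost is SAP wording and a little more analysis. The proxy already needs coverage by month, so no new data collection is expected. Reported attrition will look less favourable. The offset and the censored analysis assume that coverage loss is unrelated to event risk given the covariates (and, with weights, given the variables in the weighting model), and the report should say so.
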